1. OBJECTIVES

The objectives of our study are the following:

General:

- Check whether the technique of suboccipital inhibition influences suboccipital rachis proprioceptivity enough to modify postural balance.

Specific:

- Evaluate immediate changes in the oscillation of the center of gravity when standing after the suboccipital inhibition technique.
- Check the variation of the Romberg coefficient after the suboccipital inhibition technique.

2. STUDY DESIGN

A randomized controlled clinical trial of an explanatory, single-blind, blind appraiser strategy will be conducted (no relationship between evaluator and auditor). The subject will not know his group of belonging and, to strengthen his blinding, will not know how many measurements will be made. Participation in the study is free. The evaluation will be carried out before and immediately after the intervention.

All participants will be informed of the purpose of the study through an information document prepared for this purpose and will be clarified any doubts that may arise. After answering as many questions as necessary, the subject must sign the informed consent document to be part of the study. The principles of the Declaration of Helsinki (2004) will be respected at all times. The data collected will be treated confidentially by applying the current legislation on the protection of personal data (Organic Law 15/1999 of December 13, Protection of Personal Data) and / or any other applicable.

This study has been admitted by the Research and Ethics Committee of Cardenal Herrera CEU University Number CEI18/201

3. SUBJECTS OF STUDY

There is an increase in the prevalence of cervicalgia related to postural habits, new work practices and the use of electronic devices, traffic accidents and population aging. Cervical pain is very frequent with a point prevalence between 10-13%, appearing at some point in life up to 70% of the population. Occurs between 11-14% of sick leave. This situation justifies the feasibility of obtaining the sample required to carry out the study in an adequate time. The sample required for this project according to similar articles will be around 30 subjects per group.

The selection criteria of the sample in this study are as follows.

3.1. Inclusion criteria

The inclusion criteria will be: a) individuals who suffer neck pain for at least 3 months, b) Come to receive physiotherapy treatment at Clinica Osteomed (NRS: 8415-CV), Elche, Alicante, c) age between 18 and 65 years old, d) sign the informed consent.

3.2. Exclusion criteria

Exclusion criteria will be: a) suffering or having suffered pathologies of the postural control system (postural sensors, central nervous system or locomotor system), b) presenting deformities or orthopedic injuries in the lower limbs or rachis, d) presenting pain at the moment of study, e) present contraindications to the intervention under study, f) have received physiotherapy treatment in the last six months and g) have undergone surgical treatment of any kind.

Recruitment will be done after the first physiotherapy consultation. The physiotherapist will inform the patient of the characteristics of the study and, after checking their eligibility to participate in the study, will proceed to sign the informed consent.

4. INTERVENTION PROTOCOL

The intervention will be carried out by physiotherapists specialized in manual manipulative therapy, DO osteopaths, whose training and experience complies with the regulation of the provision of health care in osteopathy published in BOE of January 21, 2016 in the UNE-EN 16686 Standard: 2015 on "Provision of healthcare in osteopathy". The suboccipital inhibition technique is performed to release the myofascial restriction of the suboccipital region and normalize the proprioceptive afferents of the region. It is done with the patient in the supine position and the therapist sitting at the head of the bed with the elbows resting on its surface. The therapist palpates the cervical spinous processes

and slides the fingers upwards until contacting the posterior projection of the posterior arch of the atlas. Then, flexing the metacarpophalangeal at 90 degrees slowly raises the skull. The therapist's hands should remain together and the base of the skull should rest on his palms pressing with the index, middle and ring fingers of each hand in a sustained manner, but without causing pain. This pressure must be maintained during 4 minutes.

5. STUDY VARIABLES

5.1. Independent variables study object

The independent variables of the project are: a) belonging to the control or intervention group; and b) time, according to the timing of pre-intervention and post-intervention measurements. We also recorded as independent variables the general characteristics of the sample: age, BMI, sex, hours of weekly sports activity.

5.2. Dependent variables

The dependent variables of the study are Romberg index and stabilometric data with open eyes and closed eyes of the variables as follows:

- Mean of the oscillation on the X axis and on the Y axis.
- Length of the oscillation.
- Surface of the ellipse.
- Speed of the oscillation on the X axis and on the Y axis.
- Average speed of the oscillation.

6. STUDY GROUPS.

The sample will be divided into 2 groups: Intervention Group and Control Group. The suboccipital inhibition technic described will be applied to the intervention group. The control group will be given a superficial contact in the same area as the intervention, to rule out the exteroceptive effect associated with the therapist's contact. The subjects will be assigned to both groups through a computerized system of simple randomization.

7. EVALUATION.

The evaluation will be done at the Clinica Osteomed physiotherapy center located in Elche, where tools, space, evaluators and appropriately prepared interveners are available to carry out this project. The evaluation will be carried out in two moments: before the intervention and immediately after it. The time between the pre-intervention measurement and the intervention is less than 15 minutes. The time elapsed between the intervention and the post-intervention measurement will be less than 1 minute. For the evaluation a pressure platform will be used (Diagnostic Support SRL, model "Clinical MultiSensor", 4 sensors / cm², 40 captures / second) and the data will be registered by the Milletrix software (Diagnostic Support V.1.0.0.26). The stabilometric record will be made with aligned heels in a comfortable position for the subject, looking forward at eye level on a wall 5 m from the subject. On both sides there will be two clear panels that will close a 3 m wide corridor. It will remain silent, constant temperature (20°-23°) and good luminosity (2000 Lux). The stabilometric record will have a duration of 52 seconds. The measurement will be made without footwear and the orders given to the subject will be protocolized so that they do not influence their postural attitude unequally.

Stabilometric data with open eyes and closed eyes of the variables, mean of the oscillation on the X axis and on the Y axis, length of the ball, surface of the ellipse, speed of the oscillation on the X axis and on the Y axis, average speed of the oscillation and the Romberg index.

8. STUDY SEQUENCE.

The study will be carried out in two adjoining rooms with enough space to offer freedom of movement to both the examiner and the subject of study. In one of them will be the evaluator, responsible for making the measurements and collect the pre-intervention and post-intervention values, using a stabilometric platform, a scale with stadiometer and a computer. The time that elapses between the execution of the technique and the start of the post-intervention measurement is, in all cases, less than one minute. In the other room, the intervener will be in charge of performing the randomization after the first measurement and performing the corresponding intervention. It will have a treatment table for the patient and a stool for the intervener. Between both rooms there are approximately eight meters without steps or unevenness.

A. Recruitment: Recruitment will be done after the first physiotherapy consultation. The

physiotherapist will inform the patient of the characteristics of the study and, after checking their eligibility to participate in the study, will proceed to sign the informed consent.

B. Evaluation pre-intervention. The subject of the study begins his participation in the evaluation room. The evaluator performs the pre-intervention evaluation. Following the protocol of the "Association Française de Posturologie" (AFP) the subject will be in a well-lit room (2000 Lux approximately), located on the platform with the heels separated 4 cm and with the tips of the feet forming a 30° angle. You will look forward to a fixed point located 5 meters above your eyes. On both sides, two light colored panels are placed. The width of the tunnel thus formed is 3 meters. In addition the room will be silent and the temperature will be constant between 20° and 23°C so that the physiology of the subject is not altered to the point of feeling cold or sweating. We have decided to use this protocol because they are healthy subjects because, despite being an artificial position, we unify all the subjects in a position of certain instability because their heels are very close and their feet are symmetrical. Each foot is separated 15° of the sagittal plane. We will make the assessment with open eyes and closed eyes to determine the Romberg coefficient.

C. Randomization and intervention. The subjects are subjected at that moment to the randomization process. From that moment on, the sequence differs according to the group to which the individual has been assigned (control or intervention).

D. Evaluation post-intervention. A second stabilometric measurement is carried out immediately after the application of the technique, concluding the individual study.

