9. PROVIDED BENEFITS

The technique proposed in this study should have an impact on the symptoms of instability and balance disorders associated with cervicalgia. The technique under study may be included in the protocols of conservative physiotherapy treatment for patients with cervicalgia and cervicogenic instability.

Statistical Analysis Plan (SAP)

Size Sample and Feasibility

The statistical program that we will use will be SPSS v.20. To determine the sample size, a pilot study will be conducted with the same methodology as the original study to a group of 10 subjects. These subjects will be assigned to the same group. This pilot study will provide us with the estimates of the mean and variance of the response variable, thus being able to calculate the appropriate sample size by determining a minimum power value of 80% ($W > 80\%$) and a confidence level of 95% ($p < 0.05$).

The pilot sample will be part of the final sample to be studied if there are no changes in the protocol or in the variables to be measured.

For the descriptive analysis, the mean and the standard deviation will be calculated. To prove normality, the Kolmogorov-Smirnov test, or Shapiro-Wilk test, and for homoscedasticity the Levene test. To evaluate the pre-post intra-group differences, the t test will be used for related samples (if they are parametric) or the Mann-Whitney U test (if they are nonparametric). For the analysis of pre-post intergroup differences the ANOVA statistic will be used. The significance value is set at $p < 0.05$.

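### Fifteen unranked outcomes share one unadjusted 5% level, and neither the outcome behind the 80% power nor the result that answers the balance question is named

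*Combined protocol and SAP*

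**What the plan says.** Protocol section 5.2 introduces its outcomes with "The dependent variables of the study are Romberg index and stabilometric data with open eyes and closed eyes of the variables as follows". The list has mean oscillation on X and on Y, length, ellipse surface, speed on X and on Y, and average speed. Section 7 repeats it. Neither section calls any variable primary or secondary.

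Protocol section 1 has one general objective, whether the technique changes postural balance, and two specific ones: oscillation of the centre of gravity, and the Romberg coefficient. It does not say which oscillation measure or eye condition is meant. On the Romberg coefficient, section 8 (step B) says "We will make the assessment with open eyes and closed eyes to determine the Romberg coefficient", without a formula.

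The SAP says "For the analysis of pre-post intergroup differences the ANOVA statistic will be used" and, for changes within each group, "To evaluate the pre-post intra-group differences, the t test will be used for related samples" if the data are parametric. One level covers all of this: "The significance value is set at" p < 0.05. For the sample size, a ten-subject pilot is to supply "estimates of the mean and variance of the response variable", for at least 80% power. The ten are all placed in one group. The SAP adds: "The pilot sample will be part of the final sample to be studied if there are no changes in the protocol" or in the measured variables. Separately, protocol section 3 expects about 30 subjects per group, on the basis of similar articles.

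**The concern.** The trial asks one overall question, but the plan leaves open which of 15 results answers it. A 5% level controls the error of one test. It does not control the error of a conclusion that can be reached through any of several tests. The within-group tests add further routes, because nothing says that a pre-post change in the intervention group alone cannot support the conclusion.

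The sample size has the same gap. A power calculation belongs to a particular variable, and until that variable is named the calculation can be neither run nor checked. If the choice were made after the pilot, data that may enter the final sample could guide it. The pilot has two further limits. With all ten subjects in one group it cannot estimate a between-group difference, and those subjects are placed in that group rather than randomised to it.

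**Working it through.** **The plan's own figure.** About 30 per group cannot be reproduced: the documents give no effect size, standard deviation or named variable, and do not link that number to 80% power.

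**Inputs from the documents.** Outcomes (section 5.2): 7 × 2 + 1 = 15. Level (SAP): 0.05 per test, unadjusted. Two groups.

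**Assumptions.** Two-sided tests, equal allocation, one between-group test of pre-post change per variable, no true effect on any variable, and a common correlation ρ between test statistics. The documents give no correlations.

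**Chance of at least one false positive among m tests.**

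At ρ = 0: 1 − 0.95^m. For m = 15, 1 − 0.95^15 = 53.7%. For m = 2, 1 − 0.95² = 9.75%.

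At ρ > 0: 1 − ∫ φ(u) [Φ((c − √ρ·u)/√(1−ρ)) − Φ((−c − √ρ·u)/√(1−ρ))]^m du, with c = 1.96, integrated numerically.

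| ρ | 15 tests | 13 tests |
|---|---|---|
| 0 | 53.7% | 48.7% |
| 0.5 | 36.1% | 33.4% |
| 0.7 | 25.6% | 24.1% |
| 0.9 | 14.4% | 13.8% |
| 0.99 | 7.3% | 7.2% |

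The 13-test column covers the possibility that average speed is simply length over a fixed time (section 7: "The stabilometric record will have a duration of 52 seconds"), which would remove one variable per eye condition. The documents do not say how the software computes it.

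**Two endpoints, one per specific objective, each at 0.05.** 9.75% at ρ = 0 and 7.0% at ρ = 0.9.

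**Two endpoints, each at 0.025.** 1 − 0.975² = 4.9% at ρ = 0, 4.6% at 0.5 and 3.6% at 0.9.

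**Power cost, illustrative.** With 30 per group, a two-sample t test at 0.05 has 80.0% power for a standardised difference of 0.736. At 0.025 the same difference has 70.8%, and 37 per group gives 80.8%. Under Holm with equal true effects on both variables, a normal-approximation simulation gives 77% to 79% per variable for correlations from 0.9 to 0. That approximation gives about 81% unadjusted, so it is slightly optimistic. Simulated t tests (100,000 runs, 30 per group) give 75% to 77%.

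**The case against.** The strongest reply is that the harm is conditional. A reader might infer that the plan commits to declaring an effect on balance from any one significant variable, so that its error rate is 54%. The documents do not support that. No section states such a rule, a between-group analysis is planned, and if each variable were reported only for itself the rates above would describe no conclusion that the plan draws. The 54% also assumes independent tests, which is implausible for overlapping measures from the same recordings. This part of the reply stands: the rates are illustrations under a stated condition.

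A second reply is that the two specific objectives already define the endpoints. They narrow the field, but the oscillation objective still fits any of 14 variables, and two unadjusted tests would still exceed 5%.

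A third concerns the Romberg index. A reader might infer that it is undefined. The protocol ties it to the eyes-open and eyes-closed recordings, follows an external posturology protocol and names the recording software, and either of those may define it. The documents support a request to state the formula, and no more.

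Finally, a reader might infer that naming the variable would by itself make the sample-size calculation possible. It would not, because a one-group pilot supplies no between-group difference and the documents state no target.

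**Conclusion.** The concern holds. Fifteen unranked outcomes, one unadjusted level, an unnamed power variable and no decision rule mean that the stated 5% does not bound the error of an overall conclusion on balance. Under the condition that any one significant between-group result suffices, and for two-sided tests, the rate is above 5% at every correlation computed. Only that direction is firm. The size, from 7% to 54% for 15 tests, depends on assumed correlations. Reading the specific objectives as two endpoints reduces the rate to 7–10% for correlations from 0.9 to 0 but does not cure it.

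The gap in the sample-size basis does not depend on any correlation. The plan should be corrected on both counts before the pilot starts. This is an avoidable weakness; the documents do not commit to a wrong inference.

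**What to change.** Amend the SAP before any pilot measurement is seen.

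- **Primary variables.** Name two, matching the specific objectives: one oscillation variable with its eye condition, and the Romberg index with its formula. Test each between groups on pre-post change, with Holm or at 0.025 each. Alternatively name one at two-sided 0.05, accepting that the other specific objective then has no confirmatory test.
- **Everything else.** Label the remaining variables secondary or exploratory, and the within-group tests descriptive, so that neither can support the main conclusion.
- **Sample size.** Base it on the named variable or variables and a stated target between-group difference. Use the pilot for the variance only.
- **Pilot subjects.** Leave them out of the randomised comparison. Having the primary variable chosen by someone who has not seen the pilot data would not be enough, because non-randomised subjects would still be in the comparison.

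**Cost.** The change is one of wording, apart from recruiting randomised subjects in place of the ten pilot subjects and any change in the calculated size. An isolated non-primary result can no longer carry the conclusion. A single primary loses no power for that variable. With two primaries, 30 per group and a standardised difference of about 0.74, power per variable falls from 80% to about 71% at 0.025 each, and 37 per group restores 80%. Holm loses less: about 77–79% by the normal approximation, or 75–77% with simulated t tests, if both effects are equal.

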9. PROVIDED BENEFITS

The technique proposed in this study should have an impact on the symptoms of instability and balance disorders associated with cervicalgia. The technique under study may be included in the protocols of conservative physiotherapy treatment for patients with cervicalgia and cervicogenic instability.

Statistical Analysis Plan (SAP)

Size Sample and Feasibility

The statistical program that we will use will be SPSS v.20. To determine the sample size, a pilot study will be conducted with the same methodology as the original study to a group of 10 subjects. These subjects will be assigned to the same group. This pilot study will provide us with the estimates of the mean and variance of the response variable, thus being able to calculate the appropriate sample size by determining a minimum power value of 80% ($W > 80\%$) and a confidence level of 95% ($p < 0.05$).

The pilot sample will be part of the final sample to be studied if there are no changes in the protocol or in the variables to be measured.

For the descriptive analysis, the mean and the standard deviation will be calculated. To prove normality, the Kolmogorov-Smirnov test, or Shapiro-Wilk test, and for homoscedasticity the Levene test. To evaluate the pre-post intra-group differences, the t test will be used for related samples (if they are parametric) or the Mann-Whitney U test (if they are nonparametric). For the analysis of pre-post intergroup differences the ANOVA statistic will be used. The significance value is set at $p < 0.05$.

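### Sizing the trial from the pilot's observed mean and then keeping the 10 pilot subjects in unadjusted tests breaks the stated 5% error: about 7.6 to 9.1% for the within-group paired test, only 5.4 to 6.0% between groups

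*Combined protocol and SAP*

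**What the plan says.** The SAP, under Size Sample and Feasibility, plans a small pilot: "a pilot study will be conducted with the same methodology as the original study to a group of 10 subjects". On allocation it adds: "These subjects will be assigned to the same group". On its purpose: "This pilot study will provide us with the estimates of the mean and variance of the response variable". The sample size is then calculated from those estimates, "determining a minimum power value of 80"% and "a confidence level of 95"%.

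Reuse of the pilot is the default: "The pilot sample will be part of the final sample to be studied if there are no changes in the protocol" or in the measured variables.

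The final tests are a paired t test within groups (parametric case) and an ANOVA between groups, both at p < 0.05. The SAP describes no adjusted critical value, no combination test, no minimum or maximum N, and no exclusion of pilot data. It names no primary test. It also does not say which of the dependent variables in Protocol section 5.2 is the response variable used for sizing.

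Protocol section 3 gives a second basis for the sample size: about 30 subjects per group, taken from similar articles. Neither part says which basis governs.

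**The concern.** A conventional test at 5% assumes that N does not depend on the effect seen in the data being tested. Here it appears to. A pilot mean that is large by chance gives a small N, so the same 10 lucky values make up most of the final group. A pilot mean that is small by chance gives a large N, so the unlucky start is diluted. Favourable accidents are kept and unfavourable ones are averaged away.

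At stake is the false-positive rate. A technique with no effect could show a significant pre-post change more often than the 5% the plan states and, to a lesser degree, a significant difference from the superficial-contact control.

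**Working it through.** **The plan's own figure.** About 30 per group cannot be reproduced, because no effect size or SD is given. It can only be solved backwards. With two-sided 0.05 and 80% power, (1.960 + 0.842)² = 7.85, and the detectable standardised difference is √(2 × 7.85 / 30) = 0.72.

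**Inputs from the documents.** Pilot of 10, all in one group, kept in the final sample; 80% power; p < 0.05; no adjustment.

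**Assumptions, because the documents are silent.** Two-sided tests, normally distributed changes, equal final group sizes, no dropout, and a single response variable. The observed pilot mean change m is used as the target effect and the pilot SD s as the SD. Pilot and later subjects come from the same population.

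**Formulas.**
- Paired: n = 7.85 × (s/m)²
- Two-group, per group: n = 2 × 7.85 × (s/m)²

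Each is rounded up and held between a floor and a cap, which are varied because the plan gives neither.

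**How it acts (paired formula).** If m/s is 0.8 by chance, n = 7.85 / 0.64 = 12.3, so 13, and 10 of those 13 are the pilot. Its own t is already 0.8 × √10 = 2.53, above the 5% critical value of 2.26 on 9 degrees of freedom. If m/s is 0.3, n = 7.85 / 0.09 = 87.2, so 88, and the pilot is about a ninth of the group.

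**Simulation under no effect, pilot kept.** One million runs per cell, Monte Carlo standard error about 0.02 percentage points. Other runs of 200,000 to one million agree to about 0.1 point. Entries are rejection rates in percent at nominal 5%.

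| Floor per group | Cap | Paired test, paired formula | Paired test, two-group formula | Between-group test, two-group formula |
|---|---|---|---|---|
| 10 | 30 | 7.6 | 5.8 | 5.4 |
| 10 | 60 | 8.4 | 6.3 | 5.6 |
| 10 | 100 | 8.7 | 6.7 | 5.8 |
| 10 | 200 | 9.1 | 6.9 | 5.9 |
| 10 | 1000 | 9.1 | 7.0 | 6.0 |
| 30 | 60 | 5.8 | 5.6 | 5.2 |
| 30 | 1000 | 6.5 | 6.3 | 5.6 |
| 30 | 30 (fixed N) | 5.0 | 5.0 | 5.0 |

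If the paired formula also sets N for the between-group test, that test rejects 6.0 to 6.8% of the time with a floor of 10.

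**Same sizing, pilot left out of the test.** About 5.0% for both tests in every scenario. This isolates the cause: it is reuse of the pilot, not sizing from it.

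**Pilot kept, but only its SD used,** with the difference fixed in advance at 0.5, 0.74 or 1.0 SD: about 5.3 to 5.6% between groups and 5.2 to 6.4% for the paired test.

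**The case against.** The strongest case against has four parts.

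1. *The SAP gives no formula.* It never says that the observed mean change becomes the target difference. This stands as a caveat. But the SAP derives N from the pilot's mean and variance, and neither part of the document offers another target difference, so the reading is the natural one.

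2. *Section 3 already gives about 30 per group.* This stands in part. If that N is fixed, the problem is gone; if it is a minimum, the problem is small. But the SAP says the pilot determines the sample size and sets no minimum, so section 3 does not settle the matter.

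3. *The comparison that matters is between groups, and there the excess is under about 1 point (two-group formula).* This stands. The larger figures belong to the within-group test. That test is nonetheless planned at the same threshold, and no primary test is named.

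4. *Reuse is conditional.* True, but the condition is that nothing changes, so reuse is what will happen by default.

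Two stronger readings are tempting, and the documents support neither. A reader might infer that the fault persists at full size even if the pilot is randomised. For a pilot split 5/5 and sized from the observed group difference, simulation does give up to 9.3%, but no such pilot is planned. The result also depends on the sizing rule: a randomised pilot sized from the pooled mean of all 10 changes gives 4.9 to 5.0%. A reader might also infer that the error always exceeds 5%. It does not: with a change of 0.8 SD common to both groups and the paired formula, the between-group test with the one-group pilot rejects 4.6% of the time.

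**Conclusion.** The concern holds in a limited form. As the SAP is most naturally read, the stated 5% level is not the actual level. The excess is material for the within-group paired test and small for the between-group test. A floor of 30 per group shrinks it, and a fixed N of 30 per group removes it.

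The size rests on the observed pilot mean being the target effect, on the unstated formula, floor and cap, and on normal data with two-sided tests. Multiplicity across the stabilometric variables is not included. Nor is any bias from placing a non-randomised, one-group pilot inside a randomised comparison. That is a separate matter which these simulations do not measure.

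**What to change.** In the SAP, replace the sentence that adds the pilot to the final sample with: *The 10 pilot subjects are used only to calculate the sample size and are not included in any final test.* In the same edit, state whether the pilot calculation or the figure of about 30 per group in Protocol section 3 sets N, and make the two agree.

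Exclusion restores 5% for both tests whichever sizing formula is used. It also keeps the non-randomised pilot group out of the randomised comparison. The cost is a change of wording and 10 subjects who are not reused.

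Limiting the pilot to supplying the SD, with the difference fixed in advance, is not a sufficient substitute while the pilot stays in the tests: between groups it leaves an error rate much like that of the current plan.

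### Read literally, the SAP puts all 10 pilot subjects in one unnamed arm without randomisation and then counts them in the randomised comparison

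*Combined protocol and SAP*

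**What the plan says.** The SAP (Size Sample and Feasibility) makes three statements about the pilot:

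- Its conduct: "a pilot study will be conducted with the same methodology as the original study to a group of 10 subjects".
- Its allocation: "These subjects will be assigned to the same group". The group is not named.
- Its later use: "The pilot sample will be part of the final sample to be studied if there are no changes in the protocol". The same condition is set for the study variables.

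The protocol describes allocation differently:

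- Section 2: "A randomized controlled clinical trial of an explanatory, single-blind, blind appraiser strategy will be conducted".
- Section 6: "The subjects will be assigned to both groups through a computerized system of simple randomization".
- Section 8, opening paragraph: "the intervener will be in charge of performing the randomization after the first measurement".
- Section 8, step C: "The subjects are subjected at that moment to the randomization process".

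Neither Section 6 nor Section 8 exempts pilot subjects. For the final comparison the SAP says "For the analysis of pre-post intergroup differences the ANOVA statistic will be used". It does not flag pilot subjects or leave them out.

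**The concern.** A randomised comparison needs every analysed subject to have been allocated by chance. If the first 10 subjects all go to one arm by rule and stay in the analysis, two protections are lost.

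**Concurrent control.** Those 10 have no counterparts in the other arm from the same period. If early subjects respond differently from later ones, for example because the therapist or evaluator is still learning the procedure, the ANOVA cannot tell that difference from an effect of the technique.

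**Timing of allocation.** Section 8 delays randomisation until after the baseline measurement, so no allocation exists at recruitment or baseline. With one fixed pilot group, the allocation exists before both. The documents do not say whether the recruiting physiotherapist or the evaluator would know it, so this is a protection removed and not a demonstrated bias.

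The condition for carrying the pilot forward is no safeguard. It asks whether the protocol or variables changed, not whether the subjects were randomised.

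**Working it through.** **Inputs.** Pilot of 10, minimum power 80% and significance level 0.05 (SAP); about 30 per group (Section 3); simple randomisation to two groups (Section 6). Assumed, because the documents do not state them: 1:1 allocation and a two-sided test. The figure of 30 per group cannot be reproduced, since no effect size, SD or named response variable is given. It is provisional, because the SAP leaves the final size to the pilot.

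**1. Could randomisation produce a single-group pilot?** Under 1:1 simple randomisation, P(all 10 in one arm) = 2 × 0.5^10 = 0.00195, or 1 in 512. On the literal reading the SAP therefore describes a fixed assignment.

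**2. Share of one arm never randomised** = 10/n1, where n1 is the size of the arm holding the pilot.

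- Arms filled to 30:30: 10/30 = 33%.
- Other 50 simply randomised: expected arms 10 + 25 = 35 and 25, so 10/35 = 29%.
- The 95% range of a Binomial(50, 0.5) count is 18 to 32. This gives n1 from 28 to 42 (splits of 28:32 to 42:18) and a share from 10/28 = 36% down to 10/42 = 24%.

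**3. What an early-versus-late difference would do.** Let pilot subjects differ from later ones by b SD of the analysed outcome, with no treatment effect. The between-group difference is then biased by b × 10/n1. Every value of b is assumed. Type I error was simulated with 60 subjects, a two-sided test at 0.05 and 200,000 runs per cell.

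| Shift b (SD) | Bias, 30:30 | Type I error, 30:30 | Bias, 35:25 | Type I error, 35:25 | Type I error, all 60 randomised |
|---|---|---|---|---|---|
| 0.1 | 0.033 | 5.1% | 0.029 | 5.2% | 5.0% |
| 0.25 | 0.083 | 6.1% | 0.071 | 5.7% | 5.0% |
| 0.5 | 0.167 | 9.2% | 0.143 | 7.9% | 5.0% |
| 1 | 0.333 | 21.2% | 0.286 | 15.8% | 4.9% |

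If the split of the other 50 is left to chance, the figures are 5.2, 5.8, 8.0 and 16.3%. When all 60 are randomised, the same early shift falls on both arms and the mean estimate is within 0.001 SD of zero.

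**4. Power if the 10 have to be excluded.** With 30:30, a two-sample t test has 80% power at a difference of 0.736 SD (solved back from n = 30). At that difference:

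- 30:30 reduced to 20:30: power about 70%.
- 35:25 reduced to 25:25: power about 72%.

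**5. Would a pilot-status covariate rescue them?** No. With all 10 in one arm, the pilot indicator absorbs their mean completely, and the treatment coefficient equals the difference with the 10 left out. Power is practically unchanged (70.7% and 72.5%, with 57 residual df).

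**The case against.** The strongest counter-argument concerns what the sentence means. It directly follows a description of a group of 10 subjects, names no arm, and comes just after the statement that the pilot uses the main study's methodology, which includes randomisation. In a text with plainly non-native wording, it may only mean that the 10 form one pilot cohort. Then no arm is affected. This reading is possible and the documents do not exclude it. It is less natural, because Sections 6 and 8 use the same vocabulary of assignment and group for allocation to control or intervention. Staff following the sentence as written would put the first 10 subjects in one arm.

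Other points stand in part:

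- *The harm may be small.* The shifts are assumed, nothing in the documents supports a shift as large as 1 SD, and up to 0.25 SD the effect is slight. The case rests on the loss of randomisation and not on a predicted bias.
- *Stable differences cancel.* If pre-post change is analysed, a constant difference between early and later subjects drops out. What remains is a shift in the short-term change itself. This narrows the sources of bias but does not restore randomisation.
- *The covariate equivalence is exact only without other covariates.* With a baseline covariate it is approximate, and the conclusion is the same.
- *Randomising the pilot makes its means less precise.* About 5 per arm gives each arm's mean a standard error about √2 = 1.4 times that of a mean from 10. Simple randomisation splits 10 subjects 7:3 or worse with probability 352/1024 = 34%. This is a real but modest cost.

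**Conclusion.** The concern holds, and the text must be corrected before any subject is allocated. The SAP states a rule that, followed as written, conflicts with Sections 6 and 8 and places a non-randomised block without concurrent controls in one arm of a trial described as randomised. That block is 33% of the arm at 30:30, or 29% at an expected 35:25 (24–36% over the 95% range of the split). The type I error figures only illustrate the mechanism.

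Confidence is high that the passages conflict as written, and lower on which reading was intended. The consequence arises only if the pilot is run in one arm and then carried into the final sample. The percentages and power figures also depend on 1:1 allocation, a two-sided test and the provisional 30 per group.

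**What to change.** Replace the SAP sentence on pilot allocation with: *The first 10 subjects will be randomised to the two groups by the same computerised system.* This settles the text under either reading, and the 10 can stay in the analysis. If a one-arm pilot was intended, it changes the design, and the sponsor should say so openly.

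The cost is one sentence and no extra subjects. The pilot still supplies a variance, pooled over two groups on 10 − 2 = 8 df instead of 9 df in one group. The 95% limits for the true SD, as multiples of the pilot SD, become 0.68–1.92 instead of 0.69–1.83.

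If the pilot has already been run in one arm, exclude those 10 from every between-group analysis and restate the power for the randomised subjects only. If 30 per group were final, exclusion without replacement leaves about 70% power (20:30) or 72% (25:25) at the difference for which 30:30 has 80%. Replacing them costs 10 subjects. Adjusting for pilot status is not an alternative.
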